#### 13.2. Ethical Review

Lilly or its representatives must approve all ICFs before they are used at investigative sites(s). All ICFs must be compliant with the ICH guideline on GCP.

Documentation of IRB approval of the protocol and the ICF must be provided to Lilly before the study may begin at the investigative site(s). The IRB(s) will review the protocol as required.

The study site's IRB(s) should be provided with the following:

- current PI and updates during the course of the study
- ICF
- relevant curricula vitae

## 13.3. Regulatory Considerations

This study will be conducted in accordance with:

- consensus ethics principles derived from international ethics guidelines, including the Declaration of Helsinki and CIOMS International Ethical Guidelines
- International Conference on Harmonisation (ICH) GCP Guideline [E6]
- applicable laws and regulations

The investigator or designee will promptly submit the protocol to applicable IRB(s).

Some of the obligations of the sponsor will be assigned to a TPO.

An identification code assigned by the investigator to each patient will be used in lieu of the patient's name to protect the patient's identity when reporting AEs and/or other trial-related data.

#### 13.3.1. Investigator Information

Physicians with a specialty in internal medicine or diabetes will participate as investigators in this clinical trial.

#### 13.3.2. Protocol Signatures

The sponsor's responsible medical officer will approve the protocol, confirming that, to the best of his/her knowledge, the protocol accurately describes the planned design and conduct of the study.

After reading the protocol, each principal investigator will sign the protocol signature page and send a copy of the signed page to a Lilly representative.

#### 13.3.3. Final Report Signature

The clinical study report coordinating investigator will sign the final clinical study report for this study, indicating agreement that, to the best of his/her knowledge, the report accurately describes the conduct and results of the study.

An investigator will be chosen by Lilly to serve as the clinical study report coordinating investigator.

The sponsor's responsible medical officer and statistician will approve the final clinical study report for this study, confirming that, to the best of his or her knowledge, the report accurately describes the conduct and results of the study.

# Attachment 1. Protocol HMHA Study Schedule

#### Study Schedule, Protocol F1J-JE-HMHA (1413N0841)

Perform procedure as indicated.

	Perio	od 1	Period 2 Treatment			Period 3	Period 4		
Visit	Visit 1	Visit 2	Visit 3	Visit A	Visit 5	Visit 6		Visit 7	Follow up Visit 301
VISIC	Visit I Weeks	v 1811 2	v ISIT J	v 1510 4	v isit 5	VISIC U		Wook 12/	Week 14/
Wook	-2 to -1	Week 0	Wook 2	Wook 1	Wook 8	Wook 12	FD	discontinuationa	discontinuationb
VV CCK	-2 to -1	WEEKU	WCCK 2	WCCK 4	WEEK O	WCCK 12	ЕЛ	uiscontinuation	uiscontinuation~
Day	-14 to -7	Day 0	Day 14	Day 28	Day 56	Day 84	-	-	-
Allowable range	_	-	±7 days	±7 days	±7 davs	+ 7 days	+ 3 days c	+ 3 days	+ 3 davs
Patient characteristics/ diagnosis			• •••••) ~				unjo		
Consent obtainment	Y								
Patient characteristics	Y								
Diagnosis of diabetic neuropathy	Y								
Past history/ complications	Y	Y							
Treatments								•	
Drug allocation		Y							
Prescription of the investigational		Y	Y	Y	Y	Y	Y		
drugs									
Recovery of the investigational drugs/			Y	Y	Y	Y	Y	Y	
confirmation of remaining drugs									
Concomitant (previous)	Y	Y	Y	Y	Y	Y	Y	Y	
drugs/treatments				l					
Efficacy evaluation	1	1	1	1	1	1	1	[	[
24 hour every go noin									
Worst pain	<						$\rightarrow$		
Night pain									
PGI-S		Y							
PGI-I			Y	Y	Y	Y	Y		
BPI-SF		Y	Y	Y	Y	Y	Y		
BDI-II		Y		Y	Y	Y	Y		
MINI		Y							
CGI-S		Y							
CGI-I			Y	Y	Y	Y	Y		

	Perio	od 1			Period 2			Period 3	Period 4
	Scree	ning		r.	Freatment			Tapering	Follow up
Visit	Visit 1	Visit 2	Visit 3	Visit 4	Visit 5	Visit 6		Visit 7	Visit 301
	Weeks							Week 13/	Week 14/
Week	-2 to -1	Week 0	Week 2	Week 4	Week 8	Week 12	ED	discontinuation a	discontinuation b
	Day								
Day	-14 to -7	Day 0	Day 14	Day 28	Day 56	Day 84	-	-	-
							+ 3		
Allowable range	-	-	±7 days	±7 days	± 7 days	+ 7 days	daysc	+ 3 days	+ 3 days
NPSI		Y				Y	Y		
EQ-5D		Y				Y	Y		
Safety evaluation					•	•	•		
Adverse events	$\leftarrow$			-					$\longrightarrow$
Hematology/clinical chemistry	Y			Y	Y	Ye	Yf	Y	
HbA1cd	Y			Y	Y	Y	Yf	Y	
Urinalysis	Y			Y	Y		Y	Y	
CrCL	Y								
Duran un autorit	Y	The test i	s performed	l, as appropi	riate, when				
Pregnancy test		the possibility of pregnancy is suspected.							
Sitting blood pressure/heart rate	Y	Y	Y	Y	Y	Y	Y	Y	
Electrocardiographyg	Y						Y	Y	
C-SSRS	Y	Y	Y	Y	Y	Y	Y	Y	
Body weight		Y		Y		Y	Y	Y	
Fall Ouestionnaire	1	Y	Y	Y	Y	Y	Y	Y	

Abbreviations: BDI-II = Beck Depression Inventory-II; BPI-SF = Brief Pain Inventory-Short Form; CGI-I = Clinical Global Impression of Improvement; CGI-S = Clinical Global Impression of Severity; CrCL = Creatinine Clearance; C-SSRS = Columbia Suicide Severity Rating Scale; EQ-5D = EuroQol

5 Dimension; ED = Early Discontinuation; MINI = Mini-International Neuropsychiatric Interview; NPSI = Neuropathic Pain Syndrome Inventory;

NRS = numeric rating scale; PGI-I = Patient Global Impression of Improvement; PGI-S = Patient Global Impression of Severity.

- a Visit 7 occurs 7 days (+3) after Visit 6 or early discontinuation visit. Patients who discontinue the study drug without tapering do not require this visit. (See Section 9.5.1.)
- b Visit 301 occurs 7 days (+3) after Visit 7 or ED Visit without tapering.
- c ED is considered as the same day of the last administration. Variables for ED visit will be evaluated within 3 days after the last administration.
- d When there are multiple HbA1c values measured at different institutes, the value measured at the same institute at Visit 1 is used for this eligibility judgment. If both values measured by the central laboratory are available, the most recent data should be used for this eligibility judgment.
- e Glucose (fasting), Clinical chemistry only.
- f This will be applied to patients who discontinue the study without tapering.
- g ECG will be evaluated for patients who have a risk of cardiovascular events based on the investigator's decision.

#### F1J-JE-HMHA (1413N0841) (d) Clinical Protocol

# **Attachment 2. Protocol HMHA Clinical Laboratory Tests**

Clinical Laboratory Tests (collected centrally)	
Hematology:	Clinical Chemistry:
Hemoglobin	Serum Concentrations of:
Hematocrit	Sodium
Erythrocyte (red blood cell) count (RBC)	Potassium
Leukocyte (white blood cell) count (WBC)	Chloride
Neutrophils, segmented	Total bilirubin
Lymphocytes	Direct bilirubin
Monocytes	Alkaline phosphatase
Eosinophils	Alanine aminotransferase (ALT)
Basophils	Aspartate aminotransferase (AST)
Platelets	Gamma-glutamyltransferase (GGT)
	Lactate Dehydrogenase (LDH)
Urinalysis:	Total protein
Protein	Blood urea nitrogen (BUN)
Glucose	Creatinine
Blood	Uric acid
Urobilinogen	Calcium
Albumin	Glucosec
Creatinine	Albumin
Albumin- Creatinine ratio	Total cholesterol
	Low-density lipoprotein- (LDL-) cholesterol
Serum Pregnancy Test a	High-density lipoprotein- (HDL-) cholesterol
	Triglyceride (TG)
Others	Creatine kinase (CK)
Hemoglobin A1c (HbA1c)	
Creatinine clearance b	

a The serum pregnancy test applies to females of child-bearing potential (not surgically sterilized and between menarche and 1-year postmenopausal) only. Patients, who have test negative for pregnancy at the time of screening (Visit 1) based on this serum pregnancy test, are eligible for this study.

b Cockcroft-gault method will be used for estimating the Creatinine clearance.

c Glucose can be evaluated with the random glucose tests except for Visit 6.

\_

# Attachment 3. Hepatic Monitoring Tests for Treatment-Emergent Abnormality

Selected tests may be obtained in the event of a treatment-emergent hepatic abnormality and may be required in follow up with patients in consultation with the Lilly, or its designee, clinical research physician.

Hepatic Monitoring Tests (collected centrally)	
Hepatic Hematology	Haptoglobin
Hemoglobin	
Hematocrit	Hepatic Coagulation
Erythrocyte (red blood cell) count (RBC)	Prothrombin Time
Leukocyte (white blood cell) count (WBC)	Prothrombin Time, International Normalized Ratio
	(INR)
Neutrophils, segmented	
Lymphocytes	Hepatic Serologies
Monocytes	Hepatitis A antibody, total
Eosinophils	Hepatitis A antibody, immunoglobulin (Ig) M
Basophils	Hepatitis B surface antigen
Platelets	Hepatitis B surface antibody
	Hepatitis B Core antibody
Hepatic Chemistry	Hepatitis C antibody
Total bilirubin	Hepatitis E antibody, IgG
Direct bilirubin	Hepatitis E antibody, IgM
Alkaline phosphatase	
Alanine aminotransferase (ALT)	Anti-nuclear antibody
Aspartate aminotransferase (AST)	
Gamma-glutamyltransferase (GGT)	Anti-smooth muscle antibody
Creatinine kinase (CK)	

Attachment 4. Protocol Amendment F1J-JE-HMHA (1413N0841) (d) Summary [A Japan Post-marketing, Randomized, Double-blind, Parallel-group, Flexible Dose Comparative Study to Assess the Non-inferiority of Duloxetine Compared with Pregabalin in Patients with Diabetic Peripheral Neuropathic Pain]

# Overview

Protocol F1J-JE-HMHA (1413N0841) [A Japan Post-marketing, Randomized, Double-blind, Parallel-group, Flexible Dose Comparative Study to Assess the Non-inferiority of Duloxetine Compared with Pregabalin in Patients with Diabetic Peripheral Neuropathic Pain] has been amended. The new protocol is indicated by amendment (d) and will be used to conduct the study in place of any preceding version of the protocol.

The overall changes and rationale for the changes made to this protocol are as follows:

Guideline for Diabetes Management recommends both duloxetine and pregabalin as the first choice for treatment of DPNP (The Japan Diabetes Society, 2016) and the sample size was calculated assuming that the efficacies of duloxetine and pregabalin are equal because data that directly compare duloxetine and pregabalin wasn't published in a manuscript during this study's planning phase. The target number of patients has been recalculated based on the manuscripts which have been published after this study's planning phase including the randomized double-blind clinical study with DPNP to compare duloxetine and pregabalin (Bouhassira et al. 2014, Marchettini et al. 2016, Tesfaye et al. 2013) and also the results of the meta-analysis comparing them indirectly were reconsidered (Quilici et al. 2009). As the results we believe that the statistical power to confirm the non-inferiority will be maintained even after the target number of patients is reduced to 286. From the above, we decided to change the target number of patients from 410 to 286.

**Revised Protocol Sections** 

Note:	Deletions have been identified by strikethroughs.
	Additions have been identified by the use of underscore .

#### 2. Synopsis

#### Number of Planned Patients/Subjects:

```
Enrolled/Randomized: 286410 (143205 per arm)
```

#### 7.1. Summary of Study Design

Study F1J-JE-HMHA (1413N0841) is a post-marketing, Phase 4, multicenter, randomized, double-blind, parallel-group, flexible-dose, comparative study to assess the non-inferiority of duloxetine (40 to 60 mg/day) compared with pregabalin (300 to 600 mg/day) for 12 weeks in approximately 286410 adult outpatients with DPNP (143205 patients per arm).

## 12.1. Determination of Sample Size

Approximately 286410 (143205 per arm) patients will be randomized.

Sample size was calculated in order to have enough statistical power to confirm the noninferiority of duloxetine to pregabalin based on the primary endpoint, the change from baseline to Week 12 in the weekly mean of the 24-hour average pain score, which will be evaluated using an 11-point NRS in the daily patient diary. Assuming that the treatment difference of the primary endpoint is 0.1 (i.e. the efficacy of duloxetine is superior to and pregabalin by 0.1) are equal and that the common standard deviation (SD) of the primary endpoint is 1.82 with a noninferiority margin of 0.51, 141201 patients per group (282402, in total) would have a statistical power of 80% to confirm the non-inferiority with a 1-sided significance level of 0.025.

The treatment difference could be assumed to be at least 0.1 in this study based on the results such as the double-blind randomized study to comparing duloxetine and pregabalin (the treatment difference [95% confidence interval (CI)]: 0.61 [0.33, 0.90]) (Bouhassira et al. 2014, Marchettini et al. 2016, Tesfaye et al. 2013) and the results of the meta-analysis comparing them indirectly (the treatment difference [95% credible interval]: 0.25 [-0.16, 0.67]) (Quilici et al. 2009) even though there are differences such as treatment periods among the studies.

The SD was assumed to be 1.82, based on the pooled analysis results of 1 pregabalin trial and 2 duloxetine trials conducted in Japan.

The non-inferiority margin was estimated based on a meta-analysis that applied the DerSimonian Laird method. Utilizing a phase 3 trial of pregabalin in Japan, which was treated as an evaluation-test in either Japan or the US, this meta-analysis looked at the difference of variation in the average pain score between placebo and pregabalin after 12 weeks of treatment. It was estimated that the difference of the mean value and its 95% confidence interval (CI) was 1.03

(0.69, 1.37). The non-inferiority margin for the current study was set using half of the difference of the mean value, 0.51 (that is, 1.03/2). The SD was assumed to be 1.82, based on the pooled analysis results of 1 pregabalin trial and 2 duloxetine trials conducted in Japan.

6.13.5. C-SSRS Analyses	16
6.13.6. Falls Analyses	16
6.14. Subgroup Analyses	16
6.15. Interim Analyses	17
7. Unblinding Plan	18
7.1. Site Level Unblinding	18
7.2. Sponsor/Trial Level Unblinding	18

8. References19

3. Revision History

SAP Version 1 was approved prior to the first patient visit.

SAP Version 2 was approved on Jun 02, 2017 prior to the final database lock.

Significant changes were made in the following sections:

- Section 5: Update the sample size based on the protocol Amendment.
- Section 6.1: Update the sample size based on the protocol Amendment; add the rationale for the assumption of treatment difference: 0.1.
- Section 6.4: Update the “patient discontinuation of study and study treatment” to “patient discontinuation of each study period”.
- Section 6.6: Add more patient disease characteristics to be summarized.
- Section 6.10: Remove the “*” and note for “*” in the weekly mean calculation table .
- Section 6.13.2: Update “AE leading to discontinuation of study drug and/or AE leading to discontinuation of study” to “AE leading to discontinuation”.
- Section 8: Update the references.
- Section 6.5: update major protocol viloations to important protocol deviations.

4. Study Objectives

4.1. Primary Objective

The primary objective of this study is to assess the noninferiority of duloxetine (40 to 60 mg/day) compared to pregabalin (300 to 600 mg/day) after 12 weeks of treatment in patients with diabetic peripheral neuropathic pain (DPNP), as measured by change from baseline in the weekly mean of the 24-hour average pain score, which will be measured using an 11-point numeric rating scale (NRS) in the daily patient diary.

4.2. Secondary Objectives

[figure not shown]
The secondary objectives of the study are as follows:

- To compare the efficacy of duloxetine (40 to 60 mg/day, orally) versus pregabalin (300 to 600 mg/day, orally) for the treatment of patients with DPNP as measured by:
 - Patient Global Impression of Improvement (PGI-I)
 - Brief Pain Inventory-Severity and Interference rating short form (BPI-SF)
 - Weekly mean of night pain and 24-hour worst daily pain scores measured using an 11-point NRS in the daily patient diary
 - Response to treatment, defined by a 30% and 50% reduction of the weekly mean of the 24-hour average pain score measured using an 11-point NRS in the daily patient diary
 - Neuropathic Pain Symptom Inventory (NPSI)
 - Clinical Global Impressions of Improvement (CGI-I)
 - EuroQol 5 Dimension (EQ-5D)
 - Beck Depression Inventory-II (BDI-II) Total score
- To evaluate the safety and tolerability of duloxetine compared with pregabalin for the treatment of patients with DPNP as measured by frequencies of treatment-emergent adverse events (TEAEs), including edema, the discontinuation rates due to adverse events (AEs), and clinical laboratory tests (including hemoglobin A1c [HbA1c] and glucose).

5. Study Design

Study F1J-JE-HMHA (1413N0841) is a post-marketing, Phase 4, multicenter, randomized, double-blind, parallel-group, flexible-dose, comparative study to assess the noninferiority of duloxetine (40 to 60 mg/day) compared with pregabalin (300 to 600 mg/day) for 12 weeks in approximately 286 adult outpatients with DPNP (143 patients per arm).

Figure HMHA.1 illustrates the study design, which includes a screening period (approximately 1 to 2 weeks), treatment period (12 weeks), tapering period (1 week), and follow-up period (1 week). The study periods are further described below.

Dosage is shown as mg/day. Duloxetine will be administered once daily (QD) and Pregabalin will be administered twice daily (BID).

Figure HMHA.1. Illustration of study design for Clinical Protocol F1J-JE-HMHA (1413N0841).

Period 1 - Screening (1 to 2 weeks): The screening period will consist of a minimum of 7 days and a maximum of 14 days. Patients will not be allowed to use any prohibited medications and therapies from Period 1. During this period, patients will be screened for eligibility. An informed consent form (ICF) approved by an institutional review board (IRB) will be signed by the patient. Informed consent must be obtained before any study procedures are performed. During screening procedures, no study drug will be administered.

Period 2 - Treatment (12 weeks): The treatment period will begin at Visit 2 (Day 0) and end at Visit 6 (Week 12). At the beginning of Visit 2 (Day 0), patients will be randomly assigned to duloxetine or pregabalin in a 1:1 ratio. Patients will take duloxetine QD orally after breakfast and

pregabalin BID orally as instructed by each respective package label . Duloxetine will be administered at 20 mg/day for 1 week and then 40 mg/day for 3 weeks. Pregabalin will be administered at 150 mg/day for 1 week and then 300 mg/day for 3 weeks.

At Visit 4 (Week 4) and at Visit 5 (Week 8), duloxetine and pregabalin doses may be increased in patients who do not achieve ≥ 30 % pain improvement in the BPI-SF average pain score compared with baseline (Visit 2). At either week, duloxetine may be increased to 60 mg/day and pregabalin may be increased to 450 mg/day. If pregabalin is increased to 450 mg/day at Visit 4 (Week 4), it may be further increased to 600 mg/day at Visit 5 (Week 8). Patients will not be allowed to decrease their dose once increased. If patients are unable to tolerate a dosage increase during Period 2, they should be discontinued from the study.

Period 3 - Tapering (1 week): Period 3 is a 1-week tapering period to minimize discontinuation-emergent AEs. Patients receiving a final dose of duloxetine at 60 mg/day during double-blind treatment will receive 40 mg/day for the first 3 days of the 1-week tapering period and then 20 mg/day for the last 4 days. Patients receiving a final dose of duloxetine at 40 mg/day during double-blind treatment will receive 20 mg/ day throughout the 1-week tapering period. Patients receiving a final dose of pregabalin at 600 mg/day or 450 mg/day during double-blind treatment will receive 300 mg/day for the first 3 days of the 1-week tapering period and 150 mg/day for the last 4 days. Patients receiving a final dose of pregabalin at 300 mg/day during double-blind treatment will receive 150 mg/day throughout the 1 week tapering period.

Period 4 - Follow Up (1 week): During the follow-up period, no study drug will be administered. The purpose of this period is to investigate AEs that occurred 1 week after discontinuation of the study drug with or without tapering.

6. A Priori Statistical Methods

6.1. Determination of Sample Size

Approximately 286 patients will be randomized in a 1:1 ratio to duloxetine or pregabalin respectively.

Sample size was calculated in order to have enough statistical power to confirm the non-inferiority of duloxetine to pregabalin based on the primary endpoint, the change from baseline to Week 12 in the weekly mean of the 24-hour average pain score, which will be evaluated using an 11-point NRS in the daily patient diary. Assuming that the treatment difference of the primary endpoint is 0.1 (i.e. duloxetine is superior to pregabalin by 0.1) and that the common standard deviation (SD) of the primary endpoint is 1.82 with a non-inferiority margin of 0.51, 141 patients per group (282, in total) would have a statistical power of 80% to confirm the noninferiority with a 1-sided significance level of 0.025.

The treatment difference could be assumed to be at least 0.1 in this study based on the results such as the double-blind randomized study to comparing duloxetine and pregabalin (the treatment difference [95% confidence interval (CI)]: 0.61 [0.33, 0.90]) (Bouhassira et al. 2014, Marchettini et al. 2016, Tesfaye et al. 2013) and the results of the meta-analysis comparing them indirectly (the treatment difference [95% credible interval]: 0.25 [-0.16, 0.67]) (Quilici et al. 2009) even though there are differences such as treatment periods among the studies.

The noninferiority margin was estimated based on a meta-analysis that applied the DerSimonian-Laird method. Utilizing a phase 3 trial of pregabalin in Japan, which was treated as an evaluation-test in either Japan or the US, this meta-analysis looked at the difference of variation in the average pain score between placebo and pregabalin after 12 weeks of treatment. It was estimated that the difference of the mean value and its 95% CI was 1.03 (0.69, 1.37). The non-inferiority margin for the current study was set using half of the difference of the mean value, 0.51 (that is, 1.03/2). The SD was assumed to be 1.82, based on the pooled analysis results of 1 pregabalin trial and 2 duloxetine trials conducted in Japan.

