#### F1J-JE-HMHA (1413N0841) (d) Clinical Protocol

by the patient. Informed consent must be obtained before any study procedures are performed (Attachment 1). During screening procedures, no study drug will be administered.

**Period 2 - Treatment (12 weeks):** The treatment period will begin at Visit 2 (Day 0) and end at Visit 6 (Week 12). At the beginning of Visit 2 (Day 0), patients will be randomly assigned to duloxetine or pregabalin in a 1:1 ratio. Patients will take duloxetine QD orally after breakfast and pregabalin BID orally as instructed by each respective package label (See Section 9.5). Duloxetine will be administered at 20 mg/day for 1 week and then 40 mg/day for 3 weeks. Pregabalin will be administered at 150 mg/day for 1 week and then 300 mg/day for 3 weeks.

At Visit 4 (Week 4) and at Visit 5 (Week 8), duloxetine and pregabalin doses may be increased in patients who do not achieve  $\geq$ 30 % pain improvement in the BPI-SF average pain score compared with baseline (Visit 2). At either week, duloxetine may be increased to 60 mg/day and pregabalin may be increased to 450 mg/day. If pregabalin is increased to 450 mg/day at Visit 4 (Week 4), it may be further increased to 600 mg/day at Visit 5 (Week 8). See Section 9 for additional dosing details.

Based on clinical judgment and on individual patient tolerability, investigators may decide to keep patients, who don't achieve  $\geq$ 30 % pain improvement, on the original dose (dose escalation is not mandatory). However, efficacy is not expected at lower doses for patients who will not receive dosage increases. From an ethical standpoint, these patients will be considered to discontinue the study in order to select another therapy option following tapering.

Patients will not be allowed to decrease their dose once increased. If patients are unable to tolerate a dosage increase during Period 2, they should be discontinued from the study.

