## 8.3.3. Patient Discontinuation from the Study

In addition, patients will be discontinued from the study in the following circumstances:

- Enrollment in any other clinical trial involving study drug or enrollment in any other type of medical research judged not to be scientifically or medically compatible with this study
- Investigator Decision
  - The investigator decides that the patient should be discontinued from the study

- If the patient, for any reason, requires treatment with another therapeutic agent that has been demonstrated to be effective for treatment of the study indication, discontinuation from the study occurs prior to introduction of the new agent
- Subject Decision
  - The patient requests to be withdrawn from the study
- Sponsor Decision
  - Lilly, Shionogi, or its designee stops the study or stops the patient's participation in the study for medical, safety, regulatory, or other reasons consistent with applicable laws, regulations, and GCP
- Adverse Event
  - If the investigator decides that the patient should be withdrawn because of an SAE or a clinically significant laboratory value, the study drug is to be discontinued and appropriate measures are to be taken. Lilly, Shionogi, or its designee is to be alerted immediately. Refer to Safety Evaluations Section 10.4.
- The patient experiences a clinically severe AE, in the opinion of the investigator, that would preclude further participation in the study, or the patient does not tolerate the planned dosages.
- The female patient is willing to become pregnant, or becomes pregnant. The male patient is willing to have a child.
- There is a significant protocol violation, as determined by the investigator or sponsor.
- The patient answers "yes" to either Question 4 (Active Suicidal Ideation with Some Intent to Act, Without Specific Plan) or Question 5 (Active Suicidal Ideation with Specific Plan and Intent) on the "Suicidal Ideation" portion of the C-SSRS during the study period, or answers "yes" to any of the suicide-related behaviors (actual attempt, interrupted attempt, aborted attempt, preparatory act or behavior) on the "Suicidal Behavior" portion of the C-SSRS.

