# 12. Sample Size and Statistical Methods

#### 12.1. Determination of Sample Size

Approximately 286 (143 per arm) patients will be randomized.

Sample size was calculated in order to have enough statistical power to confirm the non-inferiority of duloxetine to pregabalin based on the primary endpoint, the change from baseline to Week 12 in the weekly mean of the 24-hour average pain score, which will be evaluated using an 11-point NRS in the daily patient diary. Assuming that the treatment difference of the primary endpoint is 0.1 (i.e. duloxetine is superior to pregabalin by 0.1) and that the common standard deviation (SD) is 1.82 with a non-inferiority margin of 0.51, 141 patients per group (282 in total) would have a statistical power of 80% to confirm the non-inferiority with a 1-sided significance level of 0.025.

The treatment difference could be assumed to be at least 0.1 in this study based on the results such as the double-blind randomized study to comparing duloxetine and pregabalin (the treatment difference [95% confidence interval (CI)]: 0.61 [0.33, 0.90]) (Bouhassira et al. 2014, Marchettini et al. 2016, Tesfaye et al. 2013) and the results of the meta-analysis comparing them indirectly (the treatment difference [95% credible interval]: 0.25 [-0.16, 0.67]) (Quilici et al. 2009) even though there are differences such as treatment periods among the studies.

The SD was assumed to be 1.82, based on the pooled analysis results of 1 pregabalin trial and 2 duloxetine trials conducted in Japan.

The non-inferiority margin was estimated based on a meta-analysis that applied the DerSimonian-Laird method. Utilizing a phase 3 trial of pregabalin in Japan, which was treated as an evaluation-test in either Japan or the US, this meta-analysis looked at the difference of variation in the average pain score between placebo and pregabalin after 12 weeks of treatment. It was estimated that the difference of the mean value and its 95% CI was 1.03 (0.69, 1.37). The non-inferiority margin for the current study was set using half of the difference of the mean value, 0.51 (that is, 1.03/2).

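### Does the sample-size text overstate power by giving 80% for 141 per group without a dropout assumption?

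*SAP*

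**What the plan says.** Protocol 12.1 states: "Approximately 286 (143 per arm) patients will be randomized". SAP 6.1 states that "141 patients per group (282, in total) would have a statistical power of 80% to confirm the noninferiority", at a "1-sided significance level of 0.025". The inputs in both documents are a true difference of 0.1 in favour of duloxetine, a common SD of 1.82 and a margin of 0.51. On the SD, SAP 6.1 says: "The SD was assumed to be 1.82, based on the pooled analysis results of 1 pregabalin trial and 2 duloxetine trials conducted in Japan". It also describes 1.82 as the SD of the primary endpoint, which it defines as change from baseline to Week 12 in the weekly mean of the 24-hour average pain score.

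Neither section gives a dropout rate, explains the two extra patients per arm, or says whether 141 counts randomised, full-analysis-set or Week-12-observed patients. Neither says whether 1.82 is an observed-case, LOCF or baseline-adjusted SD.

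The overview of amendment (d) in protocol Attachment 4, which cuts the target from 410 to 286, says "we believe that the statistical power to confirm the non-inferiority will be maintained even after the target number of patients is reduced to 286".

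The primary analysis (protocol 12.2.6, SAP 6.10) is an MMRM on the full analysis set with baseline pain as a covariate.

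**The concern.** The design expects some patients to leave before Week 12. SAP section 5 says: "If patients are unable to tolerate a dosage increase during Period 2, they should be discontinued from the study". Protocol 7.1 says of non-responders whose dose is not increased: "From an ethical standpoint, these patients will be considered to discontinue the study in order to select another therapy option following tapering". Protocol 8.3.3 adds that if a patient "requires treatment with another therapeutic agent that has been demonstrated to be effective for treatment of the study indication, discontinuation from the study occurs" before the new agent starts. SAP 6.3.1 has imputation rules for patients who stop because of an adverse event, death or lack of efficacy. A plan that prepares for missing Week-12 values in the analysis, but is silent on them in the power statement, appears to have computed power as if everyone finished.

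Two extra patients per arm cover only 1 − 141/143 = 1.4% loss. If dropout is larger and nothing offsets it, true power is below the stated 80%. In a trial run at the regulator's request to confirm efficacy, that would mean a greater risk of missing non-inferiority than the text suggests, and the amendment's reassurance about power would be harder to rely on. Type I error would not be affected.

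**Working it through.** **Inputs from the documents (SAP 6.1, protocol 12.1).** Margin 0.51; true advantage 0.1, so the distance to the margin is 0.51 + 0.1 = 0.61; SD 1.82; one-sided alpha 0.025; 1:1 allocation; 141 needed and 143 randomised per arm.

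**Reproducing the plan's figure.** Two-sample t test, complete data: SE = 1.82 × √(2/n), df = 2n − 2, power from the noncentral t with noncentrality 0.61/SE.

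- n = 140: SE = 0.2175, noncentrality 2.804, power 79.8%
- n = 141: SE = 0.2168, noncentrality 2.814, power 80.1%
- n = 143: SE = 0.2152, noncentrality 2.834, power 80.6%

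So 141 is the smallest n that reaches 80%. With a true difference of zero the same formula gives 201, the superseded figure in the amendment log. The documents name no formula, so the complete-data t calculation is inferred from these two exact matches.

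**Effect of dropout.** The documents give no rate, so 5 to 20% is assumed.

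*(a) Dropouts contribute nothing:* replace n by 143 × (1 − q). At q = 10%, n = 128.7.

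*(b) MMRM without baseline credit:* add the information from each dropout pattern over 12 weekly means and invert. Within-patient correlation is assumed to be compound symmetry 0.5 to 0.7, AR(1) 0.8 to 0.95, or a random intercept plus AR(1). Dropout is assumed uniform, early, or clustered after Weeks 4 and 8. The Week-12 variance rises by a factor of 1.022–1.050, 1.046–1.105, 1.072–1.167 and 1.102–1.236 at 5, 10, 15 and 20% dropout.

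*(c) MMRM with baseline credit:* if 1.82 is unadjusted and baseline correlates 0.3 with change (assumed), the variance is multiplied by 1 − 0.3² = 0.91, so the effective SD is 1.82 × √0.91 = 1.736.

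| Dropout | (a) full loss | (b) MMRM, no baseline credit | (c) MMRM, correlation 0.3 |
|---|---|---|---|
| 5% | 78.6% | 78.7–79.8% | 82.4–83.4% |
| 10% | 76.4% | 76.6–78.9% | 80.4–82.5% |
| 15% | 74.0% | 74.4–77.9% | 78.3–81.6% |
| 20% | 71.4% | 71.9–76.8% | 75.9–80.5% |

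The baseline correlation that restores 80% under the MMRM is 0.17–0.28 at 10% dropout, 0.23–0.36 at 15% and 0.28–0.42 at 20%.

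**Was power maintained by the amendment?** Compare both designs under full loss, each on its own assumed difference:

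| Dropout | 205 per arm, difference 0 | 143 per arm, advantage 0.1 |
|---|---|---|
| 0% | 80.8% | 80.6% |
| 10% | 76.6% | 76.4% |
| 15% | 74.2% | 74.0% |
| 20% | 71.6% | 71.4% |

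The gap is about 0.2 points throughout.

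**Sensitivity to the assumed advantage.** The plan treats 0.1 as a lower limit. At 15% full loss, an advantage of 0.147 restores 80%. At 0.25, the indirect estimate the plan cites, the distance is 0.76 and power at 20% full loss is 88.2%.

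**The case for a change.** The strongest case for a change is that every mitigating argument relies on something the text leaves out. Baseline adjustment helps only if 1.82 is an unadjusted SD; if it is already adjusted, that gain has been used. Partial data are already allowed for in column (b), and every structure examined there is below 80% by 5% dropout. If 1.82 is an LOCF-type SD and 141 means full-analysis-set patients, the loss may be small, but that is not stated either. The sponsor presumably knows these facts, and two or three sentences in each section would supply them.

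That stands as a criticism of the reporting. It does not establish that power is below 80%, because the same missing facts are needed to show a shortfall. The obvious correction has this difficulty too. A sentence saying that 80% holds only with complete Week-12 data, before any baseline gain, would be accurate only if 1.82 is an unadjusted, observed-case SD and 141 means patients observed at Week 12. Neither is known from the documents.

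The argument that the amendment's power claim cannot be checked does not stand. It can be checked like for like, and dropout affects the two designs almost equally. The reduction depends on the 0.1 advantage: with no true difference, 143 per arm gives 65.6% even with complete data. That is a separate question from dropout.

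**Conclusion.** This is a minor reporting gap; no arithmetic error or power shortfall has been shown. The 80% at 141 per group is correct on its stated inputs. At assumed dropout of 10 to 20%, MMRM power with 143 per arm ranges from about 72% with no baseline credit to about 82% with a baseline correlation of 0.3. Where the trial falls in that range depends on dropout, within-patient correlation and the derivation of 1.82, none of which the documents give.

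No change follows because nothing in the plan would be decided differently. The analysis model, analysis set, margin, alpha, success rule and target of 286 would all stay as they are, and the conclusion will rest on the observed confidence interval, whose width already reflects the data actually obtained. SAP Version 2 was approved on 2 June 2017, one day after the estimated last patient visit in the protocol synopsis, so restating planning power then would serve only the record. A sponsor revising the text for other reasons could usefully add the expected discontinuation rate, the population that 141 counts and the origin of 1.82.
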